## **5. SUBJECT DISPOSITION**

All subjects who provide informed consent and are randomized (NHV Cohorts 1, 2, 3, 4 and 5)/enrolled (CHB Cohorts 1b, 1c, 2b, 3b, 4b, 5b, 6, 7, 8, 9, 10,11 and 12) will be accounted for in this study. Subject disposition will be summarized using the Safety Population.

By-subject data listings for subject disposition will be generated, including informed consent date, randomization date/number (NHV cohorts), completion status, date of withdrawal and reason for withdrawal from the study, if applicable. The listing will also include the date of informed consent for CHB subjects that consented to participate in the follow-up period and the date of consent to single nucleotide polymorphisms (SNP) genetic testing and optional sampling.

The number of subjects randomized (NHV cohorts)/enrolled (CHB cohorts), as well as the number and percentage of subjects completing the study and withdrawn from the study will be presented by dose level (cohort) and overall. The reason for withdrawal will also be summarized for all subjects who do not complete the study. The table will also show the number of CHB subjects that participated in the follow-up period. Patients who participated in the follow-up period will be deemed to have completed the main part of the study (up to Day 113).

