Safety population: All participants (NHV and CHB patients) that received at least one dose of ARO-HBV or JNJ-6379.

Unless otherwise specified, for data analysis purposes baseline will be defined as pre-dose on Day 1.

Immunology Assessments (limited number of CHB patients in New Zealand only)

Immunology parameters will be summarized by cohort for the following:

- Changes in profile from pre-dose to post-dose time points for: T cell subsets (activation and exhaustion state), NK cell subsets (activation and exhaustion state), B cell subset, monocyte subsets. To be conducted if scientifically feasible.
- Changes from pre-dose to post-dose time points for: HBV antigen specific T cell response (including

HBcAg, HBsAg). To be conducted if scientifically feasible.

Virology assessments (CHB patients only)

Virologic parameters will be summarized by cohort for the following:

- Quantitative HBsAg (qHBsAg: Log change from baseline to nadir and duration of response from nadir back to approximately 20% of baseline or EOS
- Percent of patients with loss of HBsAg (defined as HBsAg < 0.05 IU/mL) at EOS and time to occurrence (Kaplan Meier)
- Percent of patients with anti-HBs seroconversion at EOS and time to occurrence (Kaplan Meier).
- Change in Anti-HBs (quantitative) over time
- Quantitative HBV DNA (when quantifiable at baseline): Log change from baseline to EOS
- Quantitative HBV RNA: Log change from baseline to nadir and duration of response from baseline to EOS (if scientifically feasible)
- Quantitative HBcrAg: Log change from baseline to nadir and duration of response from baseline to EOS
- Quantitative HBeAg (where applicable): Log change from baseline to nadir and duration of response from baseline to EOS
- Emergence of HBV mutations (sequencing of ARO-HBV target site, Core/pre-core, HBsAg epitope, any other mutations by deep sequencing)

Descriptive statistics of virologic parameters will include mean, median, count, SD, minimum, and maximum. Additional details will be provided in the statistical analysis plan.

Separate analysis will be completed for all CHB patients receiving at least one dose, all HBeAg negative patients and all HBeAg positive patients, all treatment naïve and all entecavir or tenofovir experienced patients.

Pharmacokinetics (NHV subjects and limited PK in Cohort 12):

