Once screened, eligible participants will be allocated to a sequentially numbered treatment and assigned a unique randomization number in accordance with the randomization schedule. Each participant will be assigned to either active (ARO-HBV) or PBO treatment. The allocation of active treatment or PBO will be performed using a block randomization algorithm. Randomization assignment can be requested up to 5 days prior to a scheduled Day -1 visit. Final confirmation of eligibility will be checked prior to dosing on Day 1.

Participants who drop out or are removed from the study prior to their final onsite study visit for reasons other than AEs may be replaced.

Only patients enrolled into Cohort 12 will received JNJ-6379.

8.9 *Blinding and Code-break*

Blinding of study drug (ARO-HBV)/PBO assignment is critical to the integrity of this clinical trial. It is expected that in most cases, AEs can be properly managed without the need for unblinding. However, in the event of a medical emergency in which knowledge of an individual participant's assignment is considered critical to the participant's well-being and management, the PI or documented designated treating physician may request permission to unblind the treatment assignment from the Sponsor Medical Monitor. If the situation is not an immediate emergency, the PI should contact the responsible Medical Monitor to discuss the participant and circumstances requiring the unblinding. The blind will be broken only for the specific participant under discussion. Unblinding in situations that are not an immediate emergency may only take place with the notification and agreement of the responsible Sponsor Medical Monitor. The randomization schedules will be maintained under controlled access. The personnel involved in the dispensing of investigational products will be accountable for ensuring compliance to randomization schedules. The non-blinded CRA will review the randomization schedule in comparison to the dispensing log to verify correct randomization.

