#### **4. ANALYSIS POPULATIONS**

In this study, three analysis populations are defined: Safety Population, Pharmacokinetic Population, and Pharmacodynamic population. Data for Screen Failures will not be included in any summary tables, figures, or data listings. Subjects included in the defined (various) analysis populations will be decided at the blinded data review meeting prior to unblinding of NHV cohorts. The same process will be applied to the CHB cohorts as well even if there is no blinding for these cohorts.

Furthermore, any additional analysis populations not identified in the SAP will be identified in the final CSR as post hoc analyses. This may include the addition of additional study populations or subgroups of interest.

The number and percentage of subjects in each analysis population will be summarized.

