##### *Safety Population*

All subjects who receive at least one dose of study treatment (ARO-HBV or JNJ-6379) will be included in the Safety Population. Subjects will be summarized according to the treatment they received.

All safety, treatment exposure, demographic and baseline characteristic data will be listed and summarized using the Safety Population.

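### SAP 5 promises to account for every randomised or enrolled subject, but its disposition outputs use the Safety Population, so anyone never dosed would be left out

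*SAP*

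**What the plan says.** SAP 5 opens with a wide commitment. It covers "All subjects who provide informed consent and are randomized" in the NHV cohorts, and those who consent and are enrolled in the CHB cohorts. The next sentence narrows the analysis set: "Subject disposition will be summarized using the Safety Population".

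The same section lists what the table will hold: "The number of subjects randomized (NHV cohorts)/enrolled (CHB cohorts), as well as the number and percentage of subjects completing the study and withdrawn". It adds the reason for withdrawal for every subject who does not complete.

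The Safety Population requires dosing. SAP 4: "All subjects who receive at least one dose of study treatment (ARO-HBV or JNJ-6379) will be included in the Safety Population". The Protocol synopsis agrees: "Safety population: All participants (NHV and CHB patients) that received at least one dose of ARO-HBV or JNJ-6379". No wider set exists, because in SAP 4 "three analysis populations are defined: Safety Population, Pharmacokinetic Population, and Pharmacodynamic population".

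The output lists follow the narrow sentence. SAP 19 labels Table 14.1.1.1 (disposition) as Safety. SAP 20 does the same for Listings 16.2.1.1 (enrolment), 16.2.3.1.1 (disposition) and 16.2.3.2 (randomisation).

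On timing, Protocol 8.8 says of the volunteers' allocation: "Randomization assignment can be requested up to 5 days prior to a scheduled Day -1 visit". It places the last eligibility confirmation on Day 1, before dosing.

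**The concern.** A disposition table exists to show who entered and what became of them. If its analysis set contains only dosed subjects, the row for the number randomised or enrolled can count only dosed subjects. A loss between allocation and first dose cannot appear there, nor can its reason. The randomisation listing would omit the same person, so the listings would not reveal what the table leaves out.

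What is at stake is the reporting of participant flow. A reader of the study report could not tell whether nobody went undosed or whether undosed subjects had been dropped from the count.

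This is separate from the fact that the Safety Population wording names ARO-HBV and JNJ-6379 but not placebo. The point below takes dosed placebo volunteers as included, and it remains after that wording is corrected.

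**Working it through.** **Planned numbers (context only).** SAP 2.4 gives the cohort sizes, and its totals reproduce:

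- NHV: 5 × 6 = 30.
- CHB minimum: 6 × 4 + 6 × 4 + 12 = 60, taking Cohorts 6 to 11 at their maximum of 4.
- CHB maximum: 6 × 8 + 6 × 4 + 12 = 84.

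There is no power calculation to check, and the point does not depend on one.

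**Set logic.** Let R be the number randomised or enrolled and k the number of those never dosed.

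- Set promised by the first sentence of SAP 5: R subjects.
- Set used by the second sentence and by the four outputs: R − k subjects.
- Number shown as randomised or enrolled: R − k, whatever k is.
- Undosed withdrawals shown, with reasons: 0, whatever k is.

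The two sentences agree only when k = 0.

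**Can k exceed 0?** For volunteers, yes. Assignment may be requested up to 5 days before Day −1, and Protocol 9.3.1 makes Day −1 the day before dosing. The gap can therefore be 5 + 1 = 6 days, with an eligibility check at its end. A volunteer who fails that check, or leaves in the interval, is randomised and undosed.

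**Size, by assumption on k.** The documents give no value of k, so these figures are illustrations. With R = 30 volunteers:

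| k | Shown as randomised | Shown % dosed | % dosed of all randomised |
|---|---|---|---|
| 0 | 30 | 100 | 30/30 = 100 |
| 1 | 29 | 100 | 29/30 = 96.7 |
| 2 | 28 | 100 | 28/30 = 93.3 |
| 3 | 27 | 100 | 27/30 = 90.0 |

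For completion in a single cohort, suppose 7 are randomised, 1 is never dosed and is replaced, and the 6 dosed all complete. The table shows 6/6 = 100%. On all randomised it is 6/7 = 85.7%.

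**Does another provision restore the missing subject?** Two might seem to.

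- SAP 4 promises the number and percentage in each analysis population. It states no denominator, defines no randomised or enrolled set, and has no table of its own in SAP 19.
- SAP 3 says all eCRF data will be listed. The enrolment, disposition and randomisation listings are nevertheless assigned to Safety in SAP 20. SAP 4 also keeps screen failures out of every output and does not say how a randomised volunteer who fails the Day 1 check would be classed.

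**The case against.** The strongest reply is that this is a clash of wording in which the intention is clear. SAP 5 says everyone will be accounted for, and a programmer could follow that. The study is descriptive, safety analyses properly use dosed subjects, and completion among the dosed is a legitimate summary. All of this stands, and it keeps the point small. It does not remove the point, because the population label on all four outputs follows the narrow sentence.

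A reader might be tempted to infer more than the documents support.

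- **That undosed subjects are to be expected, so the completion percentages are overstated.** The documents report no such subject and give no rate. Protocol 8.8 shows only that one is possible. The replacement rules do not settle it either: they also cover dosed subjects who drop out, and those would appear as withdrawals with reasons.
- **That the randomisation gap affects the whole trial.** It applies only to the volunteers. SAP 2.5 states that the CHB cohorts are not randomised, and Protocol 9.4 gives all of those patients active treatment. The labels would still omit a CHB patient enrolled and never dosed, but the randomisation window is no evidence that one exists.
- **That selective removal after allocation is concealed.** Volunteer allocation is double-blind. Protocol 9.3.1 requires eligibility to be documented for those included and excluded, and Protocol 8.9 and 13.1 have an unblinded monitor compare the randomisation schedule with the dispensing log. An allocated but undispensed number should be visible in those records. They are not study-report tables, so they do not repair the table, but they rule out calling the loss hidden.

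**Conclusion.** The point holds as an internal inconsistency with a definite consequence. As labelled, the four disposition outputs give a wrong count whenever someone is randomised or enrolled and not dosed, and that person's reason for leaving is not reported. The protocol makes such a case possible among the volunteers; nothing shows that it occurred.

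The size depends wholly on the unknown number undosed. With none, the outputs are identical under either set. One undosed and replaced volunteer in a cohort of otherwise complete subjects moves completion from 85.7% to 100% for that cohort. No safety, PK or PD result changes in any case.

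The conclusion assumes that the population labels in SAP 19 and 20 are applied as written and that dosed placebo volunteers count as part of the Safety Population. It is a minor reporting correction, worth making because it costs little.

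**What to change.** In SAP 4, define a further set: all randomised subjects (NHV) and all enrolled subjects (CHB), stating the event that counts as enrolment. Then:

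- In SAP 5, replace the Safety Population with this set for the disposition summary, and use its size as the denominator for the disposition percentages.
- In SAP 19 and 20, change the population label on Table 14.1.1.1 and Listings 16.2.1.1, 16.2.3.1.1 and 16.2.3.2.
- In Table 14.1.1.1, add a row for subjects randomised or enrolled but not dosed, with the reason. A row for replaced subjects is optional.

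The cost is one definition, one changed sentence, four labels and one added row with reasons. No new data collection should be needed, since SAP 5 already plans to list randomisation date and number, completion status and reason for withdrawal. If every subject was dosed, the new row reads zero and the report says so explicitly.

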## **6. PROTOCOL DEVIATIONS**

In case protocol deviations are reported, protocol deviations will be presented for each subject in the by-subject data listings.

Prior to database lock, all protocol deviations will be reviewed by medical monitors and assigned a category (see below).

A protocol deviation is defined as any intentional or unintentional change to, or noncompliance with, the approved protocol procedures or requirements. Deviations may result from the action or inaction of the patient, investigator, or site staff. All deviations will be tracked and should be reported to IRBs in accordance with their reporting policy. Examples of deviations include, but are not limited to:

- Failure to adhere to study exclusion and inclusion criteria;
- Failure to comply with dispensing or dosing requirements;
- Use of medications, food, drink, herbal remedies, or supplements that are specifically prohibited in the protocol;
- Missed or out-of-window visits;
- Drug dosing not administered within the time frame specified in the protocol;
- Failure to adhere to test requirements, including vital signs, laboratory tests, physical examinations, blood draws, medical history, etc. – either tests not done, incorrect tests done, or not done within the time frame specified in the protocol;
- Procedural deviations such as incorrect storage of study drug, failure to update the ICF when new risks become known, failure to obtain IRB/EC approvals for the protocol and ICF revisions.

## **7. DEMOGRAPHIC AND BASELINE INFORMATION**

Demographic and baseline body measurements will be summarized using the Safety Population.

### **7.1 Demographics**

Demographic data, including age, gender, race, weight, height and BMI, will be summarized by dose level (cohort) and overall. The table will also be repeated for the subset of CHB subjects that participated in the Additional Follow-up period. A by-subject data listing for demographic characteristics will be generated.

Baseline disease characteristics including, baseline alanine aminotransferase (ALT), baseline Fibroscan score, prior nucleos(t)ide (NUC) treatment status and the type of prior treatments and the log-transformed quantitative HBV DNA, genotype (if available), qHBsAg, qHBeAg, qHBcrAg, qHBV RNA (if feasible), and anti-HBsAg values and the ratio of bound/free anti-HBs (untransformed, subset of patients only) at baseline will be summarized for the CHB cohorts as well as for the subset of CHB subjects that participated in the follow-up period. The table will also be repeated for the PD Population. A by-subject data listing for baseline disease characteristics will be generated.

### **7.2 Medical history**

Past medical history will be coded using the Medical Dictionary for Regulatory Activities, MedDRA® with the latest available version. Medical history data, including the MedDRA codes, will be presented in the by-subject data listings.

### **7.3 Informed Consent and Eligibility**

Informed consent date, and inclusion/exclusion eligibility criteria information, including any criteria not met, will be listed for each subject.

### **7.4 Pregnancy Test (Urine)**

Child-bearing potential (yes/no), and if No, the reason (post menopause, surgically sterile, and other), and pregnancy test results will be included in the by-subject data listings. This includes the urine dipstick pregnancy test results assessed regularly at the scheduled study visits. Screening Follicle-Stimulating Hormone (FSH) will also be listed.

### **7.5 Serology Screen (Hepatitis/HIV)**

Data for Hepatitis B, Hepatitis C and HIV assessment at screening will be listed for each subject.

### **7.6 Urine Drug Screen**

Urine Drug Screen results at Screening will be listed for each subject.

### **7.7 Hepatic Fibrosis Measure**

The score of hepatic fibrosis at Screening will be listed for each subject.

## **8. TREATMENT EXPOSURE**

Study drug administration results will be presented using the Safety Population. Study drugs include drug administration for ARO-HBV or placebo (Placebo is only applicable for NHV Cohorts 1, 2, 3, 4 and 5), NUC and JNJ-6379 (CHB Cohort 12 only).

Each single dose of either active drug (ARO-HBV) or Placebo will be administered by subcutaneous injection (either one or two subcutaneous injections per dose as required for each dose level). Injections will be made into the subcutaneous tissue at an appropriate site (e.g. abdomen, thigh, upper arm, etc.). The abdomen is the preferred site. Injection site is to be varied (no multiple injections into the same exact site). Alternating various locations on the abdomen is acceptable, and injection site location is to be recorded in the eCRF.

A by-subject data listing will be generated for study drug (ARO-HBV or Placebo) administrations. This listing will include study drug administration date, time, dose, and injection site. If study drug was not administered, the reason why the drug was not administered will be reported. Separate listings will be created for the NUC and JNJ-6379 treatment compliance and dosing deviation data.

## 9. PHARMACOKINETICS (PK)

PK analyses will be conducted with the PK Population. PK analysis of ARO-HBV concentration-time data will be performed using validated PK software (Phoenix WinNonlin version 6.3 or higher), by a standard non-compartmental model. The actual plasma sampling times from the CRF database, i.e., the elapsed time of the blood sampling time from the dosing time, will be used for PK analysis.

PK samples will be collected for NHV Cohorts 1, 2, 3 4 and 5 on Day 1 (dosing day) at the time of 0 (pre-dose), 15 minutes, 0.5, 1, 2, 3, 6, 24 and 48 hours post-dose.

Plasma concentrations of ARO-HBV, NUC and JNJ-6379 will be measured at 2 hours post-dose on Days 1, 29 and 57 in Cohort 12 only.

